7.1.2 Other permanent discontinuation criteria

Study participants **must permanently discontinue** IMP if any of the following events occur:

1. Study participant develops an illness that would interfere with their continued participation.
2. Study participant has a significant infective episode including but not limited to bacteremia/sepsis, infectious meningitis, septic arthritis, osteomyelitis, complicated pneumonia, or visceral abscess which may or may not result in hospitalization. This list is not intended to be all inclusive, and the investigator is expected to apply their clinical judgment on continuing IMP based on the clinical situation (see Appendix 14; Section 10.14).
3. Study participant has an AE of severe or serious hypersensitivity, infusion-related reaction (Appendix 15; Section 10.15), or anaphylaxis requiring corticosteroid and/or epinephrine therapy (Sampson et al, 2006).
4. Study participant has a recurrence of aseptic meningitis (see also Appendix 13; Section 10.13).

5. Participant meets PDILI permanent discontinuation criteria (see Appendix 6, Section 10.6).
6. Study participant for whom further examinations result in a diagnosis of active TB, or if the study participant is diagnosed with LTBI with no initiation of TB preventive therapy, prematurely discontinues TB preventive therapy, or, in the opinion of the investigator or sponsor is noncompliant with TB preventive therapy. An EW visit must be scheduled as soon as possible, but not later than the next regular visit.
7. Study participant has new onset or recurrent neoplastic disease (except for superficial basal or squamous cell carcinoma of the skin not requiring targeted biological therapy, chemotherapy, or radiation).
8. Study participant has active suicidal ideation as indicated by a positive response (Yes) to either Question 4 or Question 5 of the “Since Last Visit” version of the C-SSRS. The study participant should be referred immediately to a mental healthcare professional and must be withdrawn from the study.

7.1.3 Level of follow up to be considered when permanent discontinuation from IMP occurs

In circumstances where permanent discontinuation from IMP may occur (Section 7.1.1 and Section 7.1.2), the investigator is to discuss with the study participant the appropriate processes for discontinuation from IMP and must discuss with the study participant the options for continuation of the assessments in the Schedule of Activities (Section 1.3), including different options of follow up (eg, in person, by phone/mail, in correspondence/communication with other treating physicians, from the review of medical records) and collection of data, including endpoints and AEs.

Study participants who have discontinued IMP should not be automatically removed from the study. Whenever safe and feasible, it is imperative that study participants remain on study to ensure safety surveillance and/or collection of outcome data. The investigator must document the level of follow up that is agreed to by the study participant, any changes to the scheduled visits and assessments, and the plan for follow up that is agreed to by the study participant. In regards to changes to scheduled visits, for the level of follow up, it is recommended the EOT/EW Visit and the SFU/EOS Visit be prioritized.

If the study participant does not want to continue the IMP and withdraws consent (refer to Section 7.2), investigators should contact the medical monitor, whenever possible, to discuss the withdrawal of a study participant in advance.

7.1.4 Temporary discontinuation

Study participants **must be temporarily discontinued** from the IMP if any of the following events occur:

1. The study participant develops an event of hypogammaglobulinemia with a serum total IgG reported below the lower limit of quantification (LLOQ) (currently 1.09g/L), irrespective of infection. Study participant may resume treatment when IgG level returns to $\geq 2\text{g/L}$. In view of re-initiating the IMP, additional samples will be collected to monitor study participants' IgG levels during the period of temporary discontinuation. In order to preserve the blind, additional study participants will be selected at random and requested to provide additional samples.
2. Study participant develops an event of hypoalbuminemia with serum albumin level $<2\text{g/dL}$. When the serum albumin level returns to $\geq 2.5\text{g/dL}$, the study participant may be allowed to resume treatment with IMP. Ad hoc assessments can be performed to monitor recovery of albumin levels. In view of re-initiating the IMP, additional samples will be collected to monitor study participants' serum albumin levels during the period of temporary discontinuation. In order to preserve the blind, additional study participants may be selected at random and requested to provide additional samples.

If IMP treatment is resumed, the next dose should be continued as previously scheduled. No "make up" dose is permitted. The study participant should subsequently follow the visit schedule as described in the protocol and the eCRF should be completed accordingly.

3. Study participant has a suspected drug-induced aseptic meningitis. The IMP may be restarted if clinically appropriate when signs and symptoms have resolved.

Study participants **may** be temporarily discontinued from the IMP if the following event occurs:

1. Study participant develops a nonserious persisting or recurrent infection with serum total IgG level reported between the LLOQ (currently 1.09g/L) and $<2\text{g/L}$. Upon resolution of infection and return of IgG level to $\geq 2\text{g/L}$, the study participant may be allowed to resume treatment.
2. Removed

If IMP treatment is resumed, continue the next dose as previously scheduled. No "make up" dose is permitted. The participant should subsequently follow the visit schedule as described in the protocol and the eCRF should be completed accordingly.

7.2 Participant discontinuation/withdrawal from the study

Study participants are free to withdraw from the study at any time, without prejudice to their continued care.

A study participant may withdraw from the study at any time at his/her own request, or may be withdrawn at any time at the discretion of the investigator for safety, behavioral, compliance, or administrative reasons.

If the study participant withdraws consent for disclosure of future information, the sponsor may retain and continue to use any data collected before such a withdrawal of consent.

If a study participant withdraws from the study, he/she may request destruction of any samples taken and not tested. The investigator must document this in the site study records, suspend further sample shipments, and inform the site monitor immediately.

See the Schedule of Activities (Section 1.3) for data to be collected at the time of study discontinuation and follow-up and for any further evaluations that need to be completed.

7.2.1 Study withdrawal criteria

Study participants **must be withdrawn from the study** if any of the following events occur:

1. Study participant withdraws his/her consent.
2. There is confirmation of a pregnancy during the study, as evidenced by a positive serum pregnancy test.
3. The sponsor or a regulatory agency requests withdrawal of the study participant.
4. Removed
5. Study participant has active suicidal ideation as indicated by a positive response (Yes) to either Question 4 or Question 5 of the “Since Last Visit” version of the C-SSRS. The study participant should be referred immediately to a mental healthcare professional and must be withdrawn from the study.

If a study participant withdraws from the study, the following procedures should be completed:

- The study participant should not receive further doses of IMP.
- The study participant should return for an EW Visit scheduled as soon as possible, but no later than the next scheduled visit.
- SFU or EOS Visit should be scheduled 6 weeks after the study participant has discontinued his/her IMP.

Study participants **may be withdrawn from the study**, at the discretion of the investigator, medical monitor, and study physician, if any of the following events occur:

1. Study participant is noncompliant with the study procedures or medications in the opinion of the investigator.
2. Study participant takes prohibited concomitant medications as defined in this protocol (Section 6.5.2).
3. Study participant develops an illness that would interfere with his/her continued participation.

Investigators should contact the medical monitor, whenever possible, to discuss the withdrawal of a study participant in advance.

For the study participants who are withdrawn from the study, the EOT Visit must be scheduled as soon as possible, but no later than the next regular visit. Study participants will be encouraged to complete the SFU Period.

Participants who are randomized but withdraw prior to dosing at Day 1 may be replaced. Replacement study participants will be assigned the same treatment that was assigned to the withdrawn study participant.

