Table 1-1: Schedule of Activities (through Period 1)

Procedure	Screen	Run-in	Run-in	12-week Treatment Period: 1											
Visit number	0	1	2	3	4	5	6	7	8	9	10	11	12	13	14
Visit window	up to 28 days	-	±2d	±2d	±2d	±2d	±2d	±2d	±2d	±2d	±2d	±2d	±2d	±2d	±2d
Week	-6	-2	-1	1	2	3	4	5	6	7	8	9	10	11	12
Day	-42	-14	-7	1	8	15	22	29	36	43	50	57	64	71	78
IgG binding, in vitro assay				X ^o											
Blood sampling for DNA and RNA analysis		X													
Serum complement (C3, C4) and plasma complement (C3a, C5a) ^{pq}				X											
Exploratory biomarkers		X ^{m,q}		X ^{m,q}											

ADA=anti-rozanolixizumab antibodies; BPI-SF=brief pain inventory-short form; C-SSRS=Columbia Suicidality Severity Rating Scale; d=day;

ECG=electrocardiogram; FIQR=Revised Fibromyalgia Impact Questionnaire; HBV=Hepatitis B virus; HIV=Human Immunodeficiency Virus;

Ig=immunoglobulin; IGRA=interferon gamma release assay; IMP=investigational medicinal product; NRS=numeric rating scale; pb=placebo;

PK=pharmacokinetics; PRN=pro re nata; TB=tuberculosis

Note: Assessments in the weekly columns are meant to be performed at the start of that Week prior to dosing, unless otherwise specified.

Note: The BPI-SF should be completed by the study participants in a quiet place prior to other patient-reported outcomes or protocol-specified assessments at each visit.

Note: The Baseline for each variable will be taken as the value measured prior to, but closest to, the treatment on Day 1. This may be measured on Day 1 prior to treatment or during Weeks -1 or -2 depending on the endpoint.

^a History of the completion of a pain management program should be collected when available.

^b A full C-SSRS assessment will be performed only when the study participant has a positive response to the suicidal ideation query. If a study participant has active suicidal ideation as confirmed by the answer 'Yes' to Question 4 or Question 5 of the C-SSRS assessments, the study participant will be excluded or withdrawn from the study and immediately referred to a mental healthcare professional. A C-SSRS assessment may be conducted at other visits at the discretion of the investigator.

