ⁱ Daily 24-hr pain and fatigue assessments to be collected every day for a week. Within the Screening Period, the daily average pain over the previous 24 hours will be captured using the Pain NRS through a diary over a 10-day period. Study participants require a minimum of 7 out of the 10 daily Pain NRS assessments over this 10-day period to be eligible for randomization.

^j The 24-hr pain and fatigue assessments to be collected for that day only.

^k To be performed before IMP dosing.

^l Study participants to provide their usual range doses of analgesics PRN.

^m On dosing days, PK, ADA, and IgG will be taken pre-dose.

ⁿ Total IgG only.

^o 80mL at Visit 3.

^p Samples for serum complement (C3, C4) and plasma complement (C3a, C5a) are collected predose at Visit 3 (Day 1) for all study participants. In study participants who experience an infusion reaction or hypersensitivity reaction at site, samples should also be taken 2 hours and 4 hours after the onset of the event, or otherwise as soon as possible but prior to the next dose.

^q 10mL at Visit 1 and Visit 3. In study participants who experience severe and/or serious headaches or suspected aseptic meningitis, exploratory biomarker samples should also be taken 4 hours after the onset of the event, or otherwise as soon as possible within 72 hours after the onset of the event.

Table 1-2: Schedule of Activities (Period 2 through End of Study)

Procedure	12-week Treatment Period: 2												Run-out	Run-out	EOT/EW	SFU/EOS
Visit number	15	16	17	18	19	20	21	22	23	24	25	26	27	28	-	-
Visit window	±2d	±2d	±2d	±2d	±2d	±2d	±2d	±2d	±2d	±2d	±2d	±2d	±2d	±2d	±7d	±7d
Week	13	14	15	16	17	18	19	20	21	22	23	24	25	26	28	32
Day	85	92	99	106	113	120	127	134	141	148	155	162	169	176	190	218
C-SSRS ^a	X												X		X	X
Urine pregnancy test	X				X				X				X		X	X
Laboratory assessments (full hematology, chemistry, urinalysis)	X				X				X				X		X	
Vital signs (blood pressure, pulse and temperature at every visit) ^b	X	X	X	X	X	X	X	X	X	X	X	X	X	X	X	X
Full physical examination ^c															X	X
Brief physical examination ^c	X												X			
Full neurological examination ^d															X	X
Pain NRS	X ^e	X ^e	X ^e	X ^e	X ^e	X ^e	X ^e	X ^e	X ^e	X ^e	X ^e	X ^f	X ^f	X ^e	X ^e	
BPI-SF	X				X				X				X		X	X
FIQR			X				X				X			X	X	X
Fatigue NRS	X ^e	X ^e	X ^e	X ^e	X ^e	X ^e	X ^e	X ^e	X ^e	X ^e	X ^f	X ^f	X ^f	X ^e	X ^e	
Pressure pain threshold ^g	X												X		X	X

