8.3.5 Pregnancy

Details of all pregnancies in female study participants and, if indicated, female partners of male study participants will be collected after the start of study treatment and until 90 days after the final dose.

If a pregnancy is reported, the investigator must immediately inform the sponsor within 24 hours of learning of the pregnancy and should follow the procedures outlined in Appendix 4 (Section 10.4).

The study participant should be withdrawn from the study as soon as pregnancy is known (by positive pregnancy test), and the following should be completed:

- The study participant should not receive further doses of IMP.
- The study participant should return for an EW Visit scheduled as soon as possible, but no later than the next scheduled visit.
- The study participant must be withdrawn from the study (Section 7.2.1).
- An SFU or EOS Visit should be scheduled 6 weeks after the study participant has discontinued her study medication.

Abnormal pregnancy outcomes (eg, spontaneous abortion, fetal death, stillbirth, congenital anomalies, ectopic pregnancy) are considered SAEs.

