10.2 Appendix 2: Clinical laboratory tests

- The tests detailed in the table below will be performed by the central laboratory.
- Protocol-specific requirements for inclusion or exclusion of study participants are detailed in Section 5.1 and Section 5.2 of the protocol.
- Additional tests may be performed at any time during the study as determined necessary by the investigator or required by local regulations.
- Laboratory/analyte results that could unblind the study will not be reported to investigative sites or other blinded personnel until the study has been unblinded, unless a safety alert requires a clinical review of the study participant.

Protocol-Required Safety Laboratory Assessments

Laboratory Assessments	Parameters			
Hematology	Platelet Count	RBC Indices: Mean corpuscular volume (MCV) Mean corpuscular hemoglobin (MCH) %Reticulocytes	WBC Count with Differential: Neutrophils Lymphocytes Monocytes Eosinophils Basophils	
	RBC Count			
	Hemoglobin			
	Hematocrit			
Clinical Chemistry ^a	Urea	Potassium	Aspartate Aminotransferase (AST)/Serum Glutamic-Oxaloacetic Transaminase (SGOT)	Total and direct bilirubin
	Creatinine	Sodium	Alanine Aminotransferase (ALT)/Serum Glutamic-Pyruvic Transaminase (SGPT)	Total protein ^b Albumin ^b
	Random Glucose	Calcium	Alkaline phosphatase	
	Lactate dehydrogenase (LDH)	C-reactive protein (CRP)	Low-density lipoprotein (LDL) High-density lipoprotein (HDL) Total cholesterol Triglycerides	
Routine Urinalysis	
Specific gravitypH, glucose, protein, blood, ketones, bilirubin, urobilinogen, nitrite, leukocyte esterase by dipstickMicroscopic examination (if blood or protein is abnormal)			
Other Screening Tests	
Follicle-stimulating hormone and estradiol (as needed in WOCBP only)Serum human chorionic gonadotropin pregnancy test (as needed for WOCBP)			

Laboratory Assessments	Parameters
	
 • Serology testing for Hepatitis B surface antigen, Hepatitis C virus antibody, and human immunodeficiency virus. • IGRA TB test (if applicable, as this test is optional) 
All study-required laboratory assessments will be performed by a central laboratory, with the exception of:
 
 – Urine pregnancy dipstick test^c – Urine drug screen

eCRF=electronic case report form; IEC=Independent Ethics Committee; IGRA= interferon gamma release assay

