INR=international normalized ratio; RBC=red blood cell; SAE=serious adverse event; TB=tuberculosis;

ULN=upper limit of normal; WBC=white blood cell; WOCBP=woman of childbearing potential

The results of each test must be entered into the eCRF.

^a Details of liver chemistry stopping criteria and required actions and follow-up assessments after liver stopping or monitoring event are given in Section 10.6 (Appendix 6). All events of ALT $\geq 3 \times$ ULN and bilirubin $\geq 2 \times$ ULN ($>35\%$ direct bilirubin) or ALT $\geq 3 \times$ ULN and INR > 1.5 , if INR measured, may indicate severe liver injury (possible Hy's Law) and must be reported as an SAE (excluding studies of hepatic impairment or cirrhosis).

^b The results of these assessments will not be reported to investigative sites or other blinded personnel until the study has been unblinded, unless a safety alert requires a clinical review of the study participant.

^c Urine testing will be standard for the protocol unless serum testing is required by local regulation or IEC.

Investigators must document their review of each laboratory safety report.

Other protocol-required laboratory assessments

Laboratory Assessments	Parameters
Other laboratory assessments	
 • Blood sampling for PK of rozanolixizumab^a • Blood sampling for DNA and RNA analysis^b • Serum complement (C3, C4), and plasma complement (C3a, C5a)^b • Total IgG^a • IgG subclasses^a • Anti-drug antibodies^a • Blood sampling for exploratory biomarker analysis^b

C3=complement component 3; C3a=complement component 3a; C4=complement component 4; C5a=complement component 5a; Ig=immunoglobulin; PK=pharmacokinetics

^a The results of these assessments will not be reported to investigative sites or other blinded personnel until the study has been unblinded, unless a safety alert prompts a clinical review of the study participant.

^b The results of these assessments will not be reported to investigative sites.

10.3 Appendix 3: Adverse events – Definitions and procedures for recording, evaluating, follow-up, and reporting

Definition of AE

AE definition

- An AE is any untoward medical occurrence in a patient or clinical study participant, temporally associated with the use of study medication, whether or not considered related to the study medication.

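### Sections 7.2.1 and 8.3.5 give different pregnancy-test triggers for withdrawal, and no pregnancy-specific rule says what happens to dosing between a positive urine test and serum confirmation

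*Protocol*

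**What the plan says.** Protocol Section 7.2.1 lists the events that require withdrawal from the study. One of them is: "There is confirmation of a pregnancy during the study, as evidenced by a positive serum pregnancy test".

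Section 8.3.5 covers the same event and reads: "The study participant should be withdrawn from the study as soon as pregnancy is known (by positive pregnancy test"). It then adds "The study participant should not receive further doses of IMP" and "The study participant must be withdrawn from the study (Section 7.2.1"). It does not say whether the test is urine or serum, and it does not repeat the serum condition of the section it points to.

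Appendix 4 (Section 10.4) also requires withdrawal of a participant who becomes pregnant, without naming a confirming test.

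On testing, Appendix 2 (Section 10.2) states: "Urine testing will be standard for the protocol unless serum testing is required by local regulation or IEC". In Section 1.3 the serum test is marked at Screening only. The row headed "Urine pregnancy test" supplies every later scheduled test, and Table 1-2 has no serum row. A note to both schedule tables says: "Assessments in the weekly columns are meant to be performed at the start of that Week prior to dosing, unless otherwise specified".

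**The concern.** A site that obtains a positive urine result at a dosing visit has an infusion due and two sections to consult. Under 8.3.5 the participant comes off study drug and leaves the study. Under 7.2.1 the mandatory criterion has not been met, because no serum result exists.

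Either course has a cost. If 7.2.1 is applied alone, nothing on the protocol's lists holds the dose for a possibly pregnant participant, although pregnancy is an exclusion criterion. If 8.3.5 is applied at once, an unconfirmed dipstick leads to withdrawal from a trial of about 60 people. Sites acting in good faith could differ on the same finding.

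**Working it through.** The plan states no figure on this point, so the check sets the passages side by side and then bounds the size.

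**1. The trigger**

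| Place | Test that triggers action | Action |
|---|---|---|
| 7.2.1 | Positive serum test | Mandatory withdrawal, no further study drug |
| 8.3.5 | Positive pregnancy test, type not named | Withdrawal, no further study drug |
| Appendix 4 | None named | Withdrawal |
| 7.1.2 (permanent discontinuation) | Pregnancy not listed | None |
| 7.1.4 (temporary discontinuation) | Pregnancy not listed | None |

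**2. Which test the site will have.** The scheduled on-study test is urine. A routine positive therefore fits the wording of 8.3.5, and no scheduled on-study test can satisfy 7.2.1. Appendix 2 allows serum testing where local regulation or the ethics committee demands it, but Appendix 9 records no country-specific requirement. No pregnancy passage orders a serum test after a positive urine result. The SAP (Section 5.6.6) provides for listing post-screening serum tests if any are taken, so it foresees them without requiring them.

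**3. When the results arrive.** The urine test comes before that visit's dose. On where tests are run, Appendix 2 says "All study-required laboratory assessments will be performed by a central laboratory, with the exception of" the urine pregnancy dipstick and the urine drug screen. Serum testing is therefore central. The documents give no turnaround time. That a serum result would come after the planned infusion is an inference from central testing.

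**4. Which visits matter.** Urine tests fall on dosing Visits 1, 3, 15, 19, 23 and 27 and on two later Period 1 visits. Visits 1 and 27 give placebo to everyone, and at Visit 1 eligibility is still being verified, so exclusion criterion 19 governs. Active drug may be given at Visits 3, 15, 19 and 23 and at the two later Period 1 visits. By the planned allocation, that is 20 of 60 participants in Period 1 and 20 + 20 = 40 of 60 in Period 2.

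**5. How often.** The number of women of childbearing potential is not stated. As an upper limit, assume all 60 participants are, for the full 37 weeks, at the 1% annual failure rate that Appendix 4 gives as the ceiling for correct contraceptive use:

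60 × 37/52 × 0.01 = 0.43 pregnancies.

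Appendix 4 notes that typical-use rates may differ, so this is a limit under correct use only. False-positive urine results would add to it, and the documents give no rate for them.

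**6. Effect on the primary analysis.** The Period 2 urine tests fall at Visits 15, 19, 23 and 27, which are also Brief Pain Inventory visits. That questionnaire is completed before other assessments and before dosing (Section 8.1.1). For a true pregnancy found at Visit 15, 19 or 23, that visit's score is already recorded and the next is four weeks away, so a stop date that moves by a week changes no score. At Visit 27 the last primary score is already in hand. A false positive handled differently between sites could matter more. Withdrawal at Visit 3 would cost at most the six post-baseline scores of one participant, out of 60 × 6 = 360 planned (6/360 = 1.7%).

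**The case against.** The best reply is that the two sections can be read together: 7.2.1 says what confirms a pregnancy, and 8.3.5, which cross-refers to it, says what follows. On that reading a site that stops on a urine result breaches nothing. General routes also exist. Section 7.2 lets the investigator withdraw a participant at any time for safety. Section 8 requires immediate safety concerns to be discussed with the sponsor to decide whether treatment continues. Appendix 4 allows testing whenever pregnancy is suspected.

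Part of this stands. A reader might infer that 7.2.1 permits withdrawal only on a serum result, or that it directs the site to dose meanwhile. It does neither; it is silent until a serum result exists. A reader might also infer that nothing at all covers the interval. The general routes do, though they leave the action to case-by-case judgement.

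What does not stand is that these routes remove the conflict. The parenthesis in 8.3.5 states its own trigger, and no passage says a positive urine test needs serum confirmation before pregnancy counts as known. Elsewhere the protocol does write interim rules: a positive or indeterminate tuberculosis assay stops study drug pending specialist evaluation (Section 10.12.6), and suspected meningitis requires a hold until the work-up is complete (Section 10.13). A positive urine pregnancy test has no counterpart.

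**Conclusion.** The conflict is in the current text. One positive urine result leads to immediate withdrawal under 8.3.5 and to an unmet mandatory criterion under 7.2.1, and no pregnancy-specific rule covers study drug in between. It should be corrected on grounds of participant safety and consistent conduct at the scheduled urine-test visits where active drug may be given.

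The expected number of events is small. It might be tempting to add that treatment stop dates, and so the primary intercurrent event, would vary by site. The documents do not support a material effect, given the order of assessments at the shared visits and the bounds above.

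Two points rest on inference. That 8.3.5 reaches a urine result follows from the schedule and Appendix 2, because the section does not name urine. That serum confirmation would be delayed follows from central testing, because no turnaround is stated. This review takes no position on which trigger or dosing action is right.

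**What to change.** Reconcile Sections 7.2.1 and 8.3.5 and Appendix 4, and Sections 7.1.2 and 7.1.4 if needed, so that all of them carry the same two statements: which test result triggers withdrawal, and what happens to study drug after a positive urine test and during any interval before confirmation. If serum confirmation is intended, say so in the schedule of activities and in Appendix 2. The clinical team decides the content of the rule.

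The cost is wording in the next protocol amendment and a note to sites. The statistical analysis does not change.
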